## **8.9 Withdrawal of Patients from the Study**

Patients must be withdrawn from the study for any of the following:

- Withdrawal of consent
- The patient is unwilling or unable to comply with the protocol

Other reasons for withdrawal of patients from the Study might include:

- At the discretion of the Investigator for medical reasons
- At the discretion of the Investigator or Sponsor for noncompliance
- Significant protocol deviation

All efforts will be made to complete and report the observations as thoroughly as possible up to the date of withdrawal. All information, including the reason for withdrawal from study, must be recorded in the eCRF.

Any patient who withdraws consent to participate in the study will be removed from further treatment and study observation immediately upon the date of request. These patients should be encouraged to complete the early termination study procedures and observations at the time of withdrawal (see procedures and assessments for Early Termination/Week 52/104; see [Section 8.8](#) and [Appendix A](#)).

For patients withdrawn for reasons other than withdrawal of consent, every effort should be made to complete the early termination study procedures and observations at the time of withdrawal (see procedures and assessments for Early Termination/Week 52/104; see [Section 8.8](#) and [Appendix A](#)).

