### ***8.8.1 Follow-up Visits for Early Termination from Treatment and OLE Periods***

Patients should be strongly encouraged to attend applicable landmark visits at Weeks 12, 13, 25, 26 and 50, 52 of Randomized Treatment period (calculated based on the time elapsed since Day 1) and at Weeks 64, 65, 77, 78 and 102, 104 of OLE period to collect fasting lipid panels and conduct safety assessments in accordance with the schedule of procedures in [Appendix A](#).

Any patient who discontinues early from treatment in the Randomized Treatment Period or OLE with platelet counts < LLN should be followed as per [Section 8.5.3](#) (Safety Monitoring for Platelet Count Results) and [Section 8.6.3](#) (Stopping Rules for Platelet Count Results) for the first 6 weeks after discontinuing Study Drug. Following this period, if the platelet count is stable (at least 3 consecutive values that are stable as determined by the Sponsor Medical Monitor and  $> 100,000/\text{mm}^3$ ), the next platelet count should be taken within at least 6 weeks so that patients are monitored for at least 12 weeks after discontinuing Study Drug.

If the patient declines or is unable to participate in the above, an early termination visit (Week 52 or Week 104 visit assessments) should be performed at the time of withdrawal, at a minimum, and ideally within 2 weeks from the last dose of Study Drug.

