### ***10.6.3 Efficacy Analysis (Primary and Secondary)***

The primary efficacy analysis will be the comparison of percent change from Baseline to the primary analysis time point in fasting TG between ISIS 304801 300 mg once-weekly group and placebo group in the FAS. The data will be analyzed using an analysis of covariance (ANCOVA) model with the randomization stratification factor (diagnosis of disease with or without genetics and family history) and Baseline TG as covariates. In the ANCOVA model, TG will be log-transformed. Patients with a missing primary endpoint will have TG value multiply imputed using an imputation model that contains the following variables: baseline TG, TG values at post-baseline visits and the stratification factor, and the multiple imputation will be stratified by treatment ([Schafer 1997](#); [Schafer 1999](#)). Any patient who discontinues early from the Treatment Period will be strongly encouraged to attend applicable landmark visits including Weeks 12 and 13 during which TG values will be collected and used in the primary analysis.

The primary efficacy analysis will take place after the last patient has completed the Week 52/ET visit and the database has been locked, and will be based on the percent change from Baseline in fasting TG at the primary analysis time point (end of Month 3).

A few sensitivity analyses using controlled imputations (pattern mixture models (PMM) with ANCOVA) will be conducted to assess the robustness of the primary analysis results on both the FAS and PPS. With this approach, missing not at random (MNAR) is assumed and the mean

function for the missing data from patients who discontinue the study is pre-specified in ways that assess the robustness of the MAR assumption. The mean function parameterization will be completed using the following approaches:

- Patients treated with volanesorsen who discontinue the study due to lack of efficacy or Adverse Events or other types of treatment failure will have missing post-treatment discontinuation TG values multiply imputed using estimates from the placebo patients. Specifically, the copy increment from reference (CIR) approaches will be used. Otherwise, non-informative missing data will be imputed using MI method as the same as the primary analysis

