### **3.3.5 Incomplete or Missing Data**

Patients with a missing primary endpoint will be excluded from primary efficacy analysis.

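### Protocol 8.9 ends observation, not just dosing, for patients who cannot or will not comply, and those who leave before about Day 65 then fall out of the primary analysis

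*Protocol*

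**What the plan says.** Protocol 8.8 deals with stopping study drug. Protocol 8.9 is separate and deals with leaving the study. Its mandatory list opens "Patients must be withdrawn from the study for any of the following" and has two entries: withdrawn consent, and "The patient is unwilling or unable to comply with the protocol". A second list gives grounds that may lead to withdrawal. It includes "At the discretion of the Investigator or Sponsor for noncompliance", "Significant protocol deviation" and the Investigator's medical discretion. For anyone withdrawn on a ground other than consent, "every effort should be made to complete the early termination study procedures and observations at the time of withdrawal". The sentence carries a cross-reference to 8.8.

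For patients who stop treatment early, Protocol 8.8.1 says "Patients should be strongly encouraged to attend applicable landmark visits at Weeks 12, 13, 25, 26 and 50, 52 of Randomized Treatment period". Protocol 10.6.3 repeats this for the primary endpoint: such patients "will be strongly encouraged to attend applicable landmark visits including Weeks 12 and 13 during which TG values will be collected", and those values are to be used in the primary analysis.

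Protocol 10.6.3 would have multiply imputed a missing Month 3 TG. SAP 3.3.5 replaces that: "Patients with a missing primary endpoint will be excluded from primary efficacy analysis". SAP 3.1 and 3.8 also drop the imputation and the planned sensitivity analyses. The stated reason is that study treatment was discontinued before the planned treatment period was complete.

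**The concern.** The two parts of the protocol pull in opposite directions. Sections 8.8.1 and 10.6.3 keep a patient under observation after drug stops. Section 8.9 ends observation because the patient does not or cannot comply, although 8.8 already provides for stopping drug. A site cannot tell from 8.9 whether a withdrawn patient should still be asked to attend Weeks 12 and 13.

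Adherence to a weekly TG-lowering injection plausibly affects TG, and may differ by arm: Protocol 2.3.4 gives injection-site reactions as the most frequent adverse event. If the patients removed are mainly active-arm patients with a weak response, the comparison rests on those who tolerated and took the drug. With imputation and sensitivity analyses cancelled, nothing in the planned output would show how much this matters.

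**Working it through.** **Inputs.** Week 12 window Days 65 to 82 and Week 13 window Days 83 to 106 (SAP Appendix B); one of the two visits is enough (SAP 3.2.3); on-treatment cut-off 28 days after the last dose (SAP 3.2.1); target days 78 and 85; planned change of -50% on active and -10% on placebo, SD 40, 20 per arm (Protocol 10.2, SAP 3.3.3). No document gives a withdrawal rate.

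**1. Which withdrawals lose the endpoint.** SAP 3.2.1 maps early-termination values to analysis visits. A TG taken on Days 65 to 106, within 28 days of the last dose, therefore still supplies Month 3. A last sample before Day 65 falls in the Week 8 window or earlier. The loss is thus confined mainly to withdrawal before about Day 65. For hepatic fat fraction the Month 6 window opens on Day 109, so the exposed period is longer.

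**2. What follows.** With both visits missing, Month 3 is missing (SAP 3.2.3) and the patient leaves the ANCOVA (SAP 3.3.2, 3.3.5).

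**3. Illustrative size.** The plan's own difference is -50 - (-10) = -40 points. Suppose a fraction *f* of the active arm is removed and would have changed by *m*, while those who stay average -50 and placebo averages -10:

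- all-patient active mean = (1 - *f*)(-50) + *f m*
- overstatement when they are excluded = *f*(*m* + 50)

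| Removed of 20 | *f* | *m* = -10: true difference, overstatement | *m* = -30: true difference, overstatement |
|---|---|---|---|
| 1 | 0.05 | 38, 2 | 39, 1 |
| 2 | 0.10 | 36, 4 | 38, 2 |
| 3 | 0.15 | 34, 6 | 37, 3 |
| 4 | 0.20 | 32, 8 | 36, 4 |

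For example, 3 removed at -10: (17 × -50 + 3 × -10)/20 = -44, so a true difference of 34 appears as 40.

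**4. Precision.** The plan states about 80% power at 20 per arm. A two-sided two-sample t test with difference 40 and SD 40 gives 86.9%, so the stated figure is conservative (a separate matter). Losing 2, 3 or 4 per arm gives 83.0%, 80.7% or 78.1%. Patients are not replaced (Protocol 4.3). Bias is the larger worry.

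**5. Would changing 8.9 be enough?** No. SAP 3.2.1 discards values more than 28 days after the last dose. 78 - 28 = 50 and 85 - 28 = 57, so a patient last dosed before about Day 50 loses both landmark values even after attending both visits.

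**The case against.** The case on the other side is substantial, and much of it narrows the point.

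- *A reader might infer that poor adherence forces removal.* It does not. The mandatory rule covers only patients unwilling or unable to comply; noncompliance and deviation are discretionary. Protocol 8.1 lets missed injections be rescheduled, 8.5.3 plans for interruptions during travel, and the 9-of-13-dose per protocol set in 10.3 presupposes under-dosed patients who stay in the FAS.
- *A reader might infer that platelet or adverse-event stops lead to loss through 8.9.* The documents route these through 8.6 and 8.8, with landmark visits under 8.8.1. They are not noncompliance.
- *8.9 cross-refers to 8.8, where landmark visits come first and the early-termination visit is the fallback.* This is a fair reading. Immediate removal from observation is stated only for withdrawn consent. But 8.9 itself names only early-termination procedures, so the ambiguity remains.
- *The exclusion comes from the SAP, not from 8.9.* True. These patients also remain in the FAS as defined, so 8.9 does not contradict that definition. Yet the protocol's primary imputation was stratified by treatment, so a removed active patient would have been imputed from the active arm. The placebo-based methods appeared only as sensitivity analyses, now dropped.
- *No wording can retain a patient who refuses to attend.* True. The change helps only those who still consent and can come.

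**Conclusion.** The point holds in limited form. Protocol 8.9 requires or permits an end to observation on grounds that 8.8.1 and 10.6.3 imply should end dosing only. The SAP then excludes those without a Month 3 TG and leaves no analysis to test the effect of that. The affected group is mainly patients withdrawn before about Day 65.

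The illustrative overstatement is 1 to 8 points on a 40-point difference. It assumes 1 to 4 of 20 active patients removed, responses of -10% or -30% among them, and no offsetting loss on placebo. A reader might go further and conclude that the TG, hepatic fat and HbA1c effects are in fact overstated. The documents do not support that: they give no withdrawal rate, no split by arm, and no response among those withdrawn. The direction is plausible; the size is unknown.

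**What to change.** 1. Reconcile Protocol 8.9 with 8.8.1. Noncompliance or protocol deviation alone should not end observation. Patients who still consent should be asked to attend the landmark visits (Weeks 12, 13, 25, 26, 50 and 52), whatever is decided about study drug. State that liver MRI and HbA1c are also collected at their scheduled times, since 8.8.1 names only lipid panels and safety assessments. Leave the medical-reasons discretion and all drug rules unchanged.
2. Amend SAP 3.2.1 so that the primary FAS analysis does not discard assessments more than 28 days after the last dose. Without this, many of the retained values would not count.
3. If conduct can no longer be changed, report withdrawals by 8.9 ground, arm and study day, and restore one of the protocol's placebo-based sensitivity analyses.

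The cost is amendment wording, a few extra off-drug visits, and a possibly smaller estimated effect.

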## **8.10 Concomitant Therapy and Procedures**

The use of concomitant therapies or procedures defined below must be recorded on the patient's eCRF. AEs related to administration of these therapies or procedures must also be documented on the appropriate eCRF.

### **8.10.1 Concomitant Therapy**

A concomitant therapy is any non-protocol specified drug or substance (including over-the-counter medications, herbal medications and vitamin supplements) administered between signing informed consent and completion of the post-treatment follow-up period. All concomitant medications/treatments and significant non-drug therapies (including supplements and assistive devices) received by a patient, including changes in the patient's current medications, must be recorded in the patient's source documents and CRF. Patients taking over-the-counter omega-3 fatty acids should make every effort to remain on the same brand throughout the study.

#### **Allowed Concomitant Therapy**

Any medications deemed necessary by the Investigator are allowed except those listed in the disallowed concomitant therapy.

#### **Disallowed Concomitant Therapy**

No lipid lowering therapies (e.g., fibrates, niacin, fish oil or other products containing omega-3 fatty acids [including OTC preparations], plasma apheresis), GLP-1 agonists or systemic corticosteroids may be started or adjusted after screening (except as described in [Section 8.5.6](#)) and doses of existing oral anti-diabetic medication, oral contraceptives, hormone replacement therapy, anticoagulants, or drugs or dietary supplements with potential lipid-altering effects should not be adjusted (except as described in [Sections 8.5.7](#) and [8.5.8](#)).

Study patients are prohibited from receiving other experimental agents during the study. This includes marketed agents at experimental dosages that are being tested for the treatment of hypertriglyceridemia.

Patients should consult with the Site Investigator or designee prior to initiating any new medication, including non-prescription or herbal compounds or any other non-drug therapy.

### **8.10.2 Concomitant Procedures**

A concomitant procedure is any therapeutic intervention (e.g., surgery/biopsy, physical therapy) or diagnostic assessment (e.g., blood gas measurement, bacterial cultures) performed between signing of informed consent and Week 65 visit.

#### **Disallowed Concomitant Procedure**

Plasma apheresis is not allowed during the study.

### **8.11 Treatment Compliance**

Compliance with treatment dosing is to be monitored and recorded by Study Center staff. The Study Center staff is required to document the receipt, dispensing, and return/destruction of Study Drug supplies. Patients who are self-administering Study Drug at home must record treatment in a dosing diary that will be reviewed periodically by Study Center staff and the Clinical Monitor.

## 9. SERIOUS AND NON-SERIOUS ADVERSE EVENT REPORTING

### 9.1 Sponsor Review of Safety Information

Safety information will be collected, reviewed, and evaluated by the Sponsor in accordance with the Safety Management Plan throughout the conduct of the clinical trial.

### 9.2 Regulatory Requirements

The Sponsor is responsible for regulatory submissions and reporting to the Investigators of serious adverse events (SAEs) including suspected unexpected serious adverse reactions (SUSARs) per the International Conference on Harmonization (ICH) guidelines E2A and ICH E6. Country-specific regulatory requirements will be followed in accordance with local country regulations and guidelines.

Institutional Review Boards (IRB)/Independent Ethics Committees (IEC) will be notified of any SAE according to applicable regulations. The independent DSMB will be notified of any SAE as specified in the DSMB charter.

In addition to the Investigator's assessment of relatedness, the Sponsor or designee will evaluate the available information and perform an independent assessment of relatedness. While the Sponsor may upgrade an Investigator's decision it is not permissible to downgrade the Investigator's opinion for the purposes of determining whether the SAE meets the definition of a SUSAR.

Appropriate personnel at the Sponsor will unblind SUSARs for the purpose of regulatory reporting. The Sponsor will submit SUSARs to Regulatory Agencies in blinded or unblinded fashion according to local law. The Sponsor will submit SUSARs to Investigators in a blinded fashion.

### 9.3 Definitions

#### 9.3.1 *Adverse Event*

An adverse event is any unfavorable and unintended sign (including a clinically-significant abnormal laboratory finding, for example), symptom, or disease temporally associated with the Study or use of investigational drug product, whether or not the AE is considered related to the investigational drug product.

#### 9.3.2 *Adverse Reaction and Suspected Adverse Reaction*

An adverse reaction is any AE caused by the Study Drug.

A suspected adverse reaction is any AE for which there is a reasonable possibility that the drug caused the AE. A suspected adverse reaction implies a lesser degree of certainty about causality than an adverse reaction.

### **9.3.3      *Serious Adverse Event (SAE)***

A SAE is any AE that in the view of either the Investigator or Sponsor, meets any of the following criteria:

- Results in death
- Is life threatening: that is, poses an immediate risk of death at the time of the event
- An AE or suspected adverse reaction is considered “life-threatening” if, in the view of either the Investigator or Sponsor, its occurrence places the patient at immediate risk of death. It does not include an AE or suspected adverse reaction that, had it occurred in a more severe form, might have caused death
- Requires inpatient hospitalization or prolongation of existing hospitalization
- Hospitalization is defined as an admission of greater than 24 hours to a medical facility and does not always qualify as an AE
- Results in a persistent or significant incapacity or substantial disruption of the ability to conduct normal life functions
- Results in a congenital anomaly or birth defect in the offspring of the patient (whether the patient is male or female)
- Important medical events that may not result in death, are not life-threatening, or do not require hospitalization may also be considered serious when, based upon appropriate medical judgment, they may jeopardize the patient and may require medical or surgical intervention to prevent 1 of the outcomes listed in this definition. Examples of such medical events include allergic bronchospasm requiring intensive treatment in an emergency room or at home, blood dyscrasias or convulsions that do not result in inpatient hospitalization, or the development of drug dependency or drug abuse

## **9.4      Monitoring and Recording Adverse Events**

Any pre-existing conditions or signs and/or symptoms present in a patient prior to the start of the Study (i.e., before informed consent) should be recorded as Medical History and not recorded as AEs unless the pre-existing condition worsened. The Investigator should always group signs and symptoms into a single term that constitutes a **single unifying diagnosis** if possible.

### **9.4.1      *Serious Adverse Events***

In the interest of patient safety, and in order to fulfill regulatory requirements, all SAEs (regardless of their relationship to Study Drug) should be reported to the Sponsor or designee within 24 hours of the Study Center’s first knowledge of the event. The collection of SAEs will begin after the patient signs the informed consent form and stop at the end of the patient’s follow-up period which is defined as the Week 65 visit for patients not continuing with the OLE and going straight to the Post-Treatment Follow-up period or the Week 117 visit for patients who continue with the OLE. When the Investigator is reporting by telephone, it is important to speak to someone in person versus leaving a message. An Initial Serious Adverse Event Form should be completed and a copy should be faxed to the Sponsor.

Detailed information should be actively sought and included on Follow-Up Serious Adverse Event Forms as soon as additional information becomes available. All SAEs will be followed until resolution. SAEs that remain ongoing past the patient's last protocol-specified follow-up visit will be evaluated by the Investigator and Sponsor. If the Investigator and Sponsor agree the patient's condition is unlikely to resolve, the Investigator and Sponsor will determine the follow-up requirement.

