#### **3.4.3 *OLE Period***

Following the 52-week randomized treatment period, patients will continue treatment in the OLE treatment period. The OLE period is 52 weeks as detailed in the Schedule of Procedures in Appendix A.

After a patient has been in the OLE period for a period of 3 months, an Investigator may consult with the study Medical Monitor and request that triglyceride values become unblinded to the Investigator and patient after Week 13 for the duration of the study.

Following the Week 104 of the Open-Label Extension Period, patients will have the option of continuing dosing for up to an additional 52 weeks. The schedule of procedures will follow the same schedule as the first year of OLE.

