#### **6.1.5      *OLE Post-Treatment Period***

Following the Week 52 visit of the Open-Label Extension Period, patients will have the option of continuing dosing for up to an additional 52 weeks. Patients who do not enter this option for additional dosing in the OLE period will go straight to the 13-week post-treatment follow-up period after completion of the first 52 weeks or after discontinuing treatment during the first 52 weeks of OLE. This period consists of 7 visits, as outlined in the Schedule of Procedures in [Appendix A](#).

For patients who continue to receive investigational treatment for the additional 52 weeks, the 13-week post-treatment follow-up period will follow the second year of open-label dosing.

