### ***2.1.5 OLE Post-Treatment Period***

Following the Week 52 visit of the Open-Label Extension Period, patients will have the option of continuing dosing for up to an additional 52 weeks (second OLE period). Patients who do not enter this option for additional dosing in the OLE period will go straight to the 13-week OLE post-treatment period after completion of the first 52 weeks or after discontinuing treatment during the first 52 weeks of OLE. This period consists of 7 visits, as outlined in the Schedule of Procedures in Protocol Appendix A.

For patients who continue to receive investigational treatment for the second OLE period, the 13-week OLE post-treatment period will follow completion of the Week 156 visit or after early treatment discontinuation.

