**Plasma PK Sampling Schedule**

Week	Wk 1	Wk 4	Wk 8	Wk 13	Wk 19	Wk 26	Wk 32	Wk 38	Wk 44	Wk 52
Study Day	1	22	50	85	127	176	218	260	302	358
Visit Window +/- Days	0	2	2	2	2	2	2	2	2	2
	Pre-dose									

Patients continuing to first year of OLE period

Week	Wk 56	Wk 60	Wk 65	Wk 71	Wk 78	Wk 84	Wk 90	Wk 96	Wk 104	Wk 110	Wk 117
Study Day	386	414	449	491	540	582	624	666	722	764	813
Visit Window +/- Days	2	2	2	2	2	2	2	2	2	7	7
	Pre-dose	Anytime	Anytime								

Patients continuing to second year of OLE period

Week	Wk 108	Wk 112	Wk 117	Wk 123	Wk 130	Wk 136	Wk 142	Wk 148	Wk 156	Wk 162	Wk 169
Study Day	750	778	813	855	904	946	988	1030	1086	1128	1177
Visit Window +/- Days	2	2	2	2	2	2	2	2	2	7	7
	Pre-dose	Anytime	Anytime								

Plasma concentrations of volanesorsen, along with the scheduled (nominal) and actual sampling times (i.e., time from SC dosing) will be listed (when applicable) for each patient, by treatment, patient ID, patient anti-drug antibody (ADA) status, and IM onset (if applicable) as defined in Section 3.6.2, and day. Plasma concentrations below the lower limit of quantification (LLOQ) will be presented as “0.00”.

For all patients who receive volanesorsen treatment, trough (pre-dose) and post-treatment volanesorsen plasma concentrations will be summarized by study day, with and without stratification by IM status (positive/negative or unknown), using descriptive statistics (n, mean, SD, SEM, %CV, geometric mean, geometric %CV, median, minimum, and maximum). For the purpose of calculating typical descriptive statistics for plasma concentrations, all below the lower limit of quantification (BLQ) values will be set to zero. Mean plasma concentrations that are BLQ will be presented as BLQ, and the SD and %CV will be reported as “NA” (not applicable). At the discretion of the pharmacokineticist and/or biostatistician, samples may be excluded from descriptive statistics if there are large deviations between scheduled and actual sampling times, or large deviations between actual dose and nominal dose.

Mean ( $\pm$ SD) plasma volanesorsen concentration-time plots with stratification by anti-drug antibody status will be generated on semi logarithmic scales.

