### **3.7 Safety Analyses**

Safety measures include: treatment exposure, adverse events, clinical safety lab, vital signs, physical examination, 12-Lead ECG, ECHO, concomitant medication use, and MRIs. Safety measures at Randomized Treatment Period and Randomized Treatment Period Post-Treatment Follow-up will be summarized in SAF1. Safety measures at OLE Period and OLE Post-Treatment Period will be summarized in SAF2.

Adverse events, lab shift table, and concomitant medication will be summarized by three analysis periods, including the Randomized Treatment Period using SAF1, Randomized Treatment Period Post-Treatment Follow-up among patients who do not continue to OLE using SAF1, and the combined OLE and OLE Period Post-Treatment Follow-up using SAF2. Start and end date of each analysis period is specified in the table below.

The rest safety measures will be summarized by nominal visit as collected in CRF, including vital sign, physical examination, clinical lab, Echocardiograph, ECG, and MRIs, etc.

Safety analysis period

	Period Start Date (inclusive)	Period End Date (inclusive)
Randomized Treatment Period (SAF1)	First dose date in Randomized Treatment Period	Volanesorsen group: Last dose date in the Randomized Treatment Period + one dose interval (7 days for weekly dosing schedule/ 14 days for bi-weekly dosing schedule) or first dose date in the OLE period -1 day, whichever is earlier.  Placebo group: if patient continue to OLE, end date will be first dose date of volanesorsen in the OLE period - 1 day. Otherwise, last dose date in the Randomized Treatment Period + one dose interval (7 days for weekly dosing schedule/ 14 days for bi-weekly dosing schedule)
Randomized Treatment Period Post-Treatment Follow-up (SAF1, patients who do not continue to OLE)	Last dose date in the Randomized Treatment Period + one dose interval (7 days for weekly dosing schedule/ 14 days for bi-weekly dosing schedule) + 1 day	End date of Post-Treatment Follow-up Period
Combined OLE and OLE Period Post-Treatment Follow-up (SAF2)	Volanesorsen group: Last dose date in the Randomized Treatment Period + one dosing interval (7 day for weekly dosing schedule/ 14 day for bi-weekly dosing schedule) + 1 day or first dose date in the OLE period, whichever is earlier  Placebo group: First dose date of volanesorsen in the OLE period	End date of Post-Treatment Period

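### Protocol 9.4.1 and 9.4.2 end SAE and AE collection at Week 117 for every OLE patient, although patients in the optional second OLE year are still being dosed then

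*Protocol*

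**What the plan says.** Section 9.4.1 of the protocol requires SAEs to reach the Sponsor within 24 hours of the site learning of them. Collection runs from consent to the close of the "follow-up period which is defined as the Week 65 visit" for patients who do not enter the OLE, "or the Week 117 visit for patients who continue with the OLE". Section 9.4.2 sets the same two end points for non-serious events. No third case is given.

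The rest of the protocol has a third case. Section 3.4.3 says that after Week 104 "patients will have the option of continuing dosing for up to an additional 52 weeks", on the first-year OLE schedule. Section 6.1.5 says that for these patients "the 13-week post-treatment follow-up period will follow the second year of open-label dosing".

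The SAP adds the week numbers. In its Section 2.1.5, "the 13-week OLE post-treatment period will follow completion of the Week 156 visit or after early treatment discontinuation". The sampling table in SAP 3.6.1 headed "Patients continuing to second year of OLE period" runs to Week 169. The SAP's combined OLE safety period (Section 3.7) closes at the "End date of Post-Treatment Period", with no cap at Week 117.

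Protocol Section 8.10.1 defines concomitant therapy as anything "administered between signing informed consent and completion of the post-treatment follow-up period", also without a week number.

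**The concern.** For a patient in the second OLE year, Week 117 is not the end of follow-up. It falls 13 weeks into a 52-week dosing year. A site that relied on Sections 9.4.1 and 9.4.2 alone would stop recording events while the patient was still receiving study drug.

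Two things are at stake:

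- **Reporting to the Sponsor.** Section 9.4.1 holds the general 24-hour SAE duty. Section 2.3.4 gives the context: in blinded ongoing trials, 6 of 182 dosed patients had more marked platelet falls that led to interruption or stopping of drug, and 2 of them were hospitalised with counts below 25,000/mm³. Treatment assignment is not stated.
- **The OLE safety tables.** SAP 3.7.2 reports patient frequencies and event counts for the combined OLE and follow-up period, and SAP 3.7.5 summarises exposure to the last day on drug. If collection stopped at Week 117, exposure would still be counted in full while the events were understated.

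There is also a mismatch with Section 8.10.1. A drug given for an event after Week 117 must be recorded, yet under Section 9.4 the event itself falls outside the window.

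**Working it through.** The check is calendar arithmetic on the documents' own weeks and days.

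**Inputs**
- Randomized period 52 weeks, first OLE year 52 weeks, optional second OLE year up to 52 weeks, follow-up 13 weeks (Protocol 3.4, 3.4.3, 6.1.5).
- Week 117 = Day 813, Week 156 = Day 1086, Week 169 = Day 1177 (SAP 3.6.1 sampling tables).

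**Step 1: reproduce the stated visits**
- No OLE: 52 + 13 = Week 65.
- First OLE year only: 52 + 52 + 13 = Week 117.

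Both figures are right for the pathways they fit.

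**Step 2: the pathway left out**
- End of second-year dosing: 52 + 52 + 52 = Week 156, as in SAP 2.1.5.
- End of follow-up: 156 + 13 = Week 169, as in the SAP table.
- Day check with day = 7 × (week − 1) + 1: Week 117 gives 813, Week 156 gives 1086 and Week 169 gives 1177. All three match the SAP.

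**Step 3: time after the stated cut-off for a patient who completes everything**
- On treatment: 1086 − 813 = 273 days = 39 weeks, which is 39/52 = 75% of the second year.
- Follow-up: 1177 − 1086 = 91 days = 13 weeks.
- Total: 1177 − 813 = 364 days = 52 weeks.

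**Step 4: patients who stop earlier in the second year**

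If dosing ends in Week L (105 to 156) and follow-up is completed, the uncovered time is (L + 13) − 117 = L − 104 weeks.

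| Last dosing week L | Dosing weeks uncovered | Follow-up weeks uncovered | Total |
|---|---|---|---|
| 117 | 0 | 13 | 13 |
| 130 | 13 | 13 | 26 |
| 156 | 39 | 13 | 52 |

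**Step 5: the same visit in the two SAP tables**

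For first-year OLE patients, Week 117 is the last follow-up sample, with a ±7-day window. For second-year patients it is a pre-dose sample with a ±2-day window, and their follow-up samples are at Weeks 162 and 169. Of the 11 second-year visits (108, 112, 117, 123, 130, 136, 142, 148, 156, 162, 169), 8 come after Week 117: 6 pre-dose and 2 in follow-up.

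**Step 6: other limits that do not reach the second year**

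Section 8.1 gives OLE dosing as Weeks 53–104, 8.8.1 lists landmark visits to Week 104, and 8.8.2 names Week 117 as the final follow-up visit. Section 8.10.2 ends concomitant procedures at Week 65, which falls short even of the first OLE year and so is a wider gap than the second-year omission.

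**The case against.** The best defence is that the rule is really event-based: collection ends when follow-up ends, and the week numbers only illustrate the two basic pathways. The second year repeats the first-year schedule, whose last follow-up column carries the Week 117 label (and also OLE Week 65), so a site could read the label as its final column. Weeks 156 and 169 appear as visit labels only in the SAP. The repeated schedule has an Adverse Events row, and the SAP imposes no Week 117 cut-off.

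Several other duties also carry no such cap:
- expedited reporting of platelet counts at or below 50,000/mm³ (6.2.2, 8.5.3);
- overdose and pregnancy notices (9.5.3, 9.5.4);
- minor bleeding (8.5.4);
- symptomatic hypoglycemia on the AE form (6.2.7);
- adjudication of cardiovascular and pancreatitis events (9.4.4);
- SAE notice to the ethics committee (11.3).

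Much of this stands. It shows an intent to keep collecting, and it narrows what could be lost. In particular, the lowest platelet counts would reach the Sponsor by another route. The number of patients affected is unknown, and the SAP (3.1, 3.8) records that treatment was discontinued before the planned period was completed.

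It does not remove the problem. The sentence does not leave the end of follow-up open; it defines it as Week 117 for all who continue with the OLE. The schedule row and the SAP period therefore contradict the stop and do not cancel it. None of the other duties replaces a general 24-hour SAE report to the Sponsor. The instruction to follow SAEs to resolution concerns SAEs already under report, not new ones. Early discontinuation does not make the point moot either: the same SAP keeps the second-year sampling table and defines OLE Month 18 and Month 24 time points.

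**Conclusion.** The concern holds: Sections 9.4.1 and 9.4.2 are wrong as written for patients in the second OLE year. Taken literally, they end safety collection during dosing. The uncovered time is at most 52 weeks (39 on treatment and 13 in follow-up) for a patient who completes the second year and its follow-up, and L − 104 weeks for one who stops in Week L and completes follow-up. Patients who take only the first OLE year are unaffected.

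The size rests on the SAP's Week 156 and Week 169 visits, which agree with the protocol's period lengths. The documents do not show that any site stopped at Week 117 or that any event was missed, so understated OLE counts are a risk and not a demonstrated loss. Because the defect lies in the boundary of SAE reporting itself, it must still be corrected.

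**What to change.** In Sections 9.4.1 and 9.4.2, end collection at the patient's last post-treatment follow-up visit. Then give the weeks as cases: Week 65 without the OLE, Week 117 after the first OLE year, Week 169 after a completed second year, and correspondingly earlier after early discontinuation. Section 8.10.1 already uses event-based wording of this kind.

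Reconcile the week limits in 8.1, 8.8.1, 8.8.2 and 8.10.2 with 3.4.3 and 6.1.5. For 8.10.2, cover the first OLE year as well.

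The cost is one sentence in each of two sections, week-number corrections in four others, and a notice to sites. No visits are added, because the repeated first-year schedule already includes adverse events. If any patient has already passed Week 117 on second-year dosing, ask those sites to confirm that later events were recorded.
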